2.0 OBJECTIVES

2.1 Primary Objective

To determine whether patient-specific mutations correlate with clinical overall response to decitabine in patients with AML or MDS.

2.2 Secondary Objectives

- To determine whether 10 consecutive days per cycle of decitabine improves outcomes compared with historical controls treated with 5 consecutive days per cycle of decitabine.
- To determine whether other biomarkers correlate with clinical overall response to decitabine in patients with AML or MDS. These will include:
 1. The velocity and depth of patient-specific mutation clearance;
 2. The bone marrow expression profile and change in expression profile during decitabine treatment;
 3. The decrease in bone marrow methylcytosine content in response to decitabine.

3.0 PATIENT SELECTION

3.1 Inclusion Criteria

All of the following:

- Patient must have non-M3 AML or MDS
- An adverse risk karyotype defined by:
 - Complex karyotype by cytogenetics, or
 - Deletion of all or part of chromosome 5, 7, 12, or 17 defined by FISH or cytogenetics, or
 - Somatic TP53 mutation

All of the following:

1. Patient must have an ECOG performance status ≤ 2 .
2. Patient must have $>10\%$ disease burden measured by cytomorphology, flow cytometry, or cytogenetics.
3. Patient must have peripheral white blood cell count $\leq 50,000/\text{mcl}$.
4. Patient must have adequate organ function, defined as:
 - a. Total bilirubin $\leq 1.5 \times \text{ULN}$
 - b. AST/ALT $\leq 2.5 \times \text{ULN}$
 - c. Serum creatinine $\leq 2.0 \times \text{ULN}$
5. Patient must have undergone ≤ 2 cycles of prior hypomethylating agent (decitabine or azacitidine).
6. Patient must be enrolled in HRPO# 201011766 (“Tissue Acquisition for Analysis of Genetic Progression Factors in Hematologic Diseases”).
7. Patient must be ≥ 18 years of age.
8. Patient must be able to understand and willing to sign an IRB-approved written informed consent document.

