Because all patient-specific exome-discovered mutations will be assessed a second time in the primary bone marrow sample as well as the Cycle 1 Day 10 \pm 1, Cycle 1 Day 28 \pm 4, and Cycle 2 Day 28 \pm 4 bone marrow samples, this study will also serve to validate all exome-discovered mutations. This is important, because exome sequencing is associated with a 20-50% false-discovery rate depending on type I error tolerated (mutation-calling algorithms are typically set for greater sensitivity than specificity). Thus, many mutations discovered during exome sequencing are incorrect. This second analysis of these mutations will serve to exclude these false positive calls.

3. To correlate the bone marrow expression profile from pre-study and Cycle 1 Day 10 \pm 1 with response to decitabine.

We will correlate expression signatures, and changes in expression signatures, with:

- Achievement of clinical CR,
- Mutation status.

4. To correlate the extent of bone marrow DNA hypomethylation on Cycle 1 Day 10 \pm 1 with response to decitabine.

We will assess the percent reduction in bone marrow methylcytosine content using LC-MS. Patients will be evaluated pre-study and Cycle 1 Day 10 \pm 1. The change in DNA methylcytosine content will be correlated to:

- Achievement of clinical CR,
- Change in expression signature.

This will determine whether inadequate blast exposure to decitabine correlates with drug resistance.

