3.2 Exclusion Criteria

1. Patient must not be pregnant or nursing.
2. The patient must not have acute promyelocytic leukemia or t(15;17) observed by FISH.
3. Patient must not have known CNS leukemia.
4. Patient must not have a history of positive HIV serology.
5. Patient must not have a history of positive Hepatitis C serology.
6. Patient must not have undergone a prior allogeneic stem cell transplant.
7. Patient must not have any uncontrolled intercurrent illness including, but not limited to, ongoing or active infection, ongoing or active GVHD, congestive heart failure of NYHA class 3 or 4, unstable angina pectoris, cardiac arrhythmia, or psychiatric illness/social situation that would limit compliance with study requirements.
8. Patient must not have had radiation therapy within 14 days of enrollment.
9. Patient must not have received any chemotherapy within 21 days of enrollment, and any acute treatment-related toxicities must have returned to baseline. Patients

may be receiving hydra at time of enrollment.

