5.2 Study Procedures

5.2.1 Pre-study Procedures

Pre-study procedures must take place no more than 14 days prior to the first dose of decitabine except where noted below.

1. Bone marrow aspirate and biopsy. Standard bone marrow procurement procedures will be followed for collection of the tissue. Assessments performed on bone marrow will include correlative studies (collected under HRPO# 201011766), morphologic assessment, cytogenetics, and FISH.
2. Bone marrow or peripheral blood for flow cytometry
3. Skin biopsy sample (collected under HRPO# 201011766). There is no required time frame for this sample; it may have been collected months or even years prior to the first dose of decitabine.

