5.4 Concomitant Therapy and Supportive Care Guidelines

5.4.1 Chemotherapy

Patients cannot receive any chemotherapy within 21 days of study enrollment and must have recovered from any treatment-related toxicities. However, patients may be receiving hydrea at enrollment and may continue on hydrea through Cycle 2 of decitabine. An indication for hydrea following 2 cycles of decitabine is evidence that the patient is not responding and decitabine should be discontinued. Other than decitabine, patients cannot receive chemotherapy during this trial.

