14.2.3 Secondary Endpoint Analyses

The overall response rate (CR/CRi/PR) and complete response rate (CR/CRi) will be compared with historical controls[2], and the 95% confidence intervals will be provided.

The rate of patient specific mutation clearance after 10, 28, and 56 days of therapy will be determined using an Illumina based platform. We will compare the rate of mutation clearance between the patients who achieve a CR/CRi after 4 cycles and those who do not. We anticipate that we will identify between 6 and 25 exonic SNVs per case (the range obtained with >200 AML samples sequenced to date with whole genome or exome sequencing), and that the expected 95% confidence interval of the mean variant allele frequency will be $\pm 2.56\%$ and $\pm 1.25\%$,

respectively, if we assume an anticipated standard deviation of 3.2% within the same clone. The change of tumor burden over time and its association with clinical response will be assessed using 2-way ANOVA for repeated measurement data, followed by the ad-hoc multiple comparisons for between-group differences (e.g., responders vs. non-responders) at given time points as well as the between-time differences within each group. The resultant critical P values will also be corrected using permutation analysis for multiple testing.

The percent decrease in bone marrow methylcytosine will be calculated on day 10 ± 1 . We will compare this reduction with previously published data and between the patients who achieve CR/CRi and those who do not. The correlation of peak plasma levels of decitabine with response will be assessed using 2-sample t-test or Mann-Whitney non-parametric rank-sum test as appropriate. The change of total bone marrow DNA methylcytosine from baseline and its association with both steady-state plasma drug levels and response will be assessed using 2-way ANOVA for repeated measurement data, followed by the ad-hoc multiple comparisons for between-group differences (e.g., responders vs. non-responders) and between-time differences. Similar analyses will be performed for the correlation of expression profiles and SNP analysis with pharmacokinetic data.

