Appendix 2 Study Flow Chart

Study Flow Chart

Test	Pre-study ¹	Base-line ²	All Cycles Day 1	All Cycles Days 1-10 ³	Cycle 1 Day 4 ± 1	Cycle 1 Day 10 ± 1 and 28 ± 4	Every week	Every 2 weeks	Even cycles Day 28±4	End of Study
Informed Consent	X									
Medical History		X								
Physical Exam		X ^a	X ^b							X
Transfusion Requirements ^c		X ^c	Ongoing							
Bone Marrow Aspirate and Biopsy	X ^d					X ^d			X ^d	X ^d
Flow Cytometry ^c	X									
Pregnancy test		X								
CBC with differential and platelets		X	X				X ^f			X
Serum Chemistries ^g		X	X					X ^f		X
Decitabine administration ^h				X						
Adverse Events			Ongoing							
Post-study follow-up										X ⁱ

¹ To be performed within 28 days of the first dose of decitabine.

² To be performed within 7 days of the first dose of decitabine.

³ Decitabine may be reduced to Days 1-5 or Days 1-3. See Section 6.3 for details.

^a To include height, weight, and ECOG.

^b To include weight.

^c Care should be given to record the frequency of transfusions from 8 weeks prior to first dose of study drug through the duration of the study.

^d Bone marrow biopsy and aspirate should be performed at baseline, at Cycle 1 Day 10 ± 1, and at Day 28 ± 4 of Cycles 1, 2, 4 and 6 for clinical disease assessment. Patients who achieve with clinical response (CRi or better) and are receiving cycles every 6 weeks, will undergo bone marrow biopsies on day 42 ± 4. Following Cycle 6, bone marrow biopsies should be performed at the discretion of the treating physician to assess for relapse or progression. Standard bone marrow procurement procedures will be followed for collection of the tissue. To include: correlative studies (collected under HRPO# 201011766), morphologic assessment, cytogenetics and FISH at all time points. A skin biopsy sample (collected under HRPO# 201011766) is required at pre-study, but may have been collected months or even years prior to first dose of decitabine.

^e On bone marrow or peripheral blood.

^f After Cycle 1, these labs may be obtained every other week (CBC) or once a month (Chemistries) at the discretion of the treating physician.

^g Serum chemistries include bicarbonate, calcium, glucose, total protein, albumin, BUN, potassium, chloride, sodium, creatinine, total bilirubin, AST, ALT, alkaline phosphatase, and LDH.

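### Prior hypomethylating treatment is allowed but not separated in the methylcytosine comparison, so if it differs by response it can create or weaken an apparent exposure-resistance link

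*Combined protocol and SAP*

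**What the plan says.** **Eligibility.** Section 3.1 requires no more than two "cycles of prior hypomethylating agent (decitabine or azacitidine"). The only stated treatment-free interval for drugs is in Section 3.2: "Patient must not have received any chemotherapy within 21 days of enrollment". It does not name hypomethylating agents. Section 5.4.1 says "Other than decitabine, patients cannot receive chemotherapy during this trial", which suggests that decitabine counts as chemotherapy under that rule; azacitidine is not addressed.

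**Baseline.** Section 1.3 says "We will assess the percent reduction in bone marrow methylcytosine content using LC-MS", comparing the pre-study marrow with Cycle 1 Day 10. Section 5.2.1 sets the timing of that marrow: "Pre-study procedures must take place no more than 14 days prior to the first dose of decitabine except where noted below". A footnote to the Appendix 2 flow chart says instead "To be performed within 28 days of the first dose of decitabine".

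**Analysis.** Section 14.2.3 says "The percent decrease in bone marrow methylcytosine will be calculated on day" 10 ± 1. It compares the decrease between patients who do and do not achieve CR/CRi, and plans a two-way repeated-measures ANOVA. No term for prior treatment is named. The subgroups in Section 14.2.5 are age, cytogenetics and four-gene mutation status. Section 14.2.2 plans a logistic model with demographic and clinical covariates, but does not list them.

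**Interpretation.** Section 1.3 concludes: "This will determine whether inadequate blast exposure to decitabine correlates with drug resistance".

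**The concern.** A percent reduction has the baseline as its denominator. If earlier decitabine or azacitidine has already lowered marrow methylcytosine, a patient who reaches a given Day-10 level shows a smaller percent fall than an untreated patient who reaches the same level. That patient looks under-exposed to study drug when the baseline is the cause.

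This affects the responder comparison only if prior exposure is also unevenly spread by response. Either direction is plausible. Patients refractory to earlier cycles may be over-represented among non-responders, which would create or inflate an exposure-resistance association. Patients already part-way to a response may be over-represented among responders, which would weaken a real one. The plan has no step that would reveal either.

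Clearance raises a related but different issue. Pre-exposed patients may start from lower allele frequencies. Clones cleared before the pre-study sample would not be found by exome sequencing and so would not be tracked. Depth of response, defined as the lowest allele frequency reached, is also open to this.

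**Working it through.** **Inputs from the documents (Section 14.2.3).** 45 responders, 55 non-responders, target difference 20 points, SD 15, alpha 0.05, two-sample t-test. Two-sided testing is assumed, because sidedness is not stated for this test.

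**1. The plan's own figure.** Standard error = 15 × √(1/45 + 1/55) = 3.015. Noncentrality = 20 / 3.015 = 6.63 on 98 df. Power exceeds 99.99%, so the stated 99% is reproduced and is conservative. The smallest observed difference that reaches significance is 1.984 × 3.015 = 5.98 points.

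**2. How close the baseline can be to prior treatment.** Assume that the 21-day rule covers the prior agent and that dosing starts on the day of enrollment. With the 14-day window the marrow can fall 21 − 14 = 7 days after the last prior dose. With the 28-day window, 21 − 28 = −7: it can precede that dose by up to 7 days. Twenty-one days is a minimum; no maximum is given, so other patients may have been exposed long before.

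**3. Effect on one patient.** Measured reduction = 100 × (1 − D/B), where D is the Day-10 level and B the baseline, both as fractions of the untreated (native) level. Assume D = 0.50 whatever the baseline.

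| Baseline B | Measured reduction | Shortfall from 50 |
|---|---|---|
| 1.0 | 50.0% | 0 |
| 0.9 | 44.4% | 5.6 |
| 0.8 | 37.5% | 12.5 |
| 0.7 | 28.6% | 21.4 |

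**4. Effect on the group difference.** Spurious difference = shortfall × (pre-exposed share in non-responders − share in responders). Assume 40% and 10%, with no true difference. The SD is inflated for the mixture of exposed and naive patients.

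| Baseline B | Spurious difference | Chance of a significant result |
|---|---|---|
| 0.9 | 0.30 × 5.6 = 1.7 points | 8% |
| 0.8 | 0.30 × 12.5 = 3.75 points | 21% |
| 0.7 | 0.30 × 21.4 = 6.4 points | 44% |

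With equal shares (25% in each group) the spurious difference is 0 and the error rate stays at 5%.

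**5. When a true 20-point difference exists.** Suppose 50% of responders and 10% of non-responders are pre-exposed, with a 20-point shortfall. The mean difference falls to 20 − 0.40 × 20 = 12 points, and power is still 93.5%. The mean difference drops below 5.98 only if shortfall × imbalance exceeds 20 − 5.98 = 14.0 points. It changes sign only if that product exceeds 20.

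**6. Alternative drug model.** If decitabine removes a fixed proportion of what is present, then D = 0.5 × B and the measured reduction is 50% at every baseline. The artefact is zero.

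**7. Cost of a naive-only analysis.** Remove half of each group, leaving 22 and 28: standard error = 15 × √(1/22 + 1/28) = 4.27, noncentrality = 20 / 4.27 = 4.68 on 48 df, power 99.6%. With 60% removed (18 and 22), power is 98.3%.

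**The case against.** The strongest reply is that every quantity driving the bias is assumed: the pre-exposed share, its split by response, the residual level, and a Day-10 level that does not depend on the baseline. Under a proportional drug effect nothing happens. At baselines of 90 or 80% of native the spurious difference in the example is below the 5.98-point significance threshold. This is also one secondary comparison in a single-arm phase II biomarker study. All of this stands; it limits the size that can be claimed, but the plan still has no way to tell which case applies.

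A reader might also infer stronger things that the documents do not support.

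- *That carry-over could reverse the conclusion.* A change of sign needs shortfall × imbalance above 20 points, which cannot happen with shortfalls up to 20 points. With a 30-point shortfall it needs an imbalance above 20/30, or 67 percentage points.
- *That every pre-exposed patient's baseline is a mid-treatment sample.* Section 3.2 sets a minimum interval, not a maximum.
- *That clearance velocity is biased in the same way.* Section 1.3 defines it as a natural-log rate. Under exponential clearance that rate does not depend on the starting level.
- *That response itself is distorted by the baseline.* AML CR/CRi and MDS CR use absolute blast thresholds (Sections 9.1 and 9.2). Only AML PR, MDS marrow CR and MDS PR need a fall of at least 50%, and a lowered baseline makes that harder to reach. Section 3.1 also requires more than 10% disease burden at entry.
- *That the primary mutation-response test is confounded.* That would require prior exposure to be related to mutation status, which nothing in the documents shows. The planned logistic model has room for prior exposure but does not name it.

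**Conclusion.** The point holds as a foreseeable, unhandled confounder of one stated secondary inference. Prior hypomethylating exposure is permitted, the possibly post-exposure marrow is the denominator, and the result is to be read as evidence about drug exposure and resistance.

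The size cannot be fixed from the documents. Under the fixed Day-10 model with a 10% versus 40% split, the spurious difference is about 1.7 to 6.4 points, or 8 to 32% of the 20-point target. With no true difference, that raises the false-positive rate to between 8% and 44%. Bias requires both residual hypomethylation at baseline and unequal exposure by response; without either it is nil. A true 20-point difference would usually still be detected. The stated 99% power is not in error. For clearance, the concern is limited to starting allele frequency, already-cleared clones and depth. This is a cheap improvement to the analysis and does not invalidate the design.

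**What to change.** **Section 14.2.3.** Analyse the methylcytosine comparison, and clearance depth, in hypomethylating-naive patients; or adjust for prior exposure using agent, number of cycles (0 versus 1–2) and time since last dose. Time since last dose matters because a simple 0 versus 1–2 split treats exposure three weeks ago and long ago alike. Report the all-patient result alongside.

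**Section 14.2.2.** Name prior hypomethylating exposure among the clinical covariates of the logistic model already planned.

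**Data.** The inclusion worksheet (Section 15.0) and baseline medical history (Section 5.2.2) already cover prior treatment. Agent, cycles and last-dose date should be recorded explicitly. The text should also state whether the 21-day rule covers azacitidine as well as decitabine.

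**Consistency.** The 14-day window in Section 5.2.1 and the 28-day window in the Appendix 2 flow chart must be reconciled.

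**Cost.** Analysis wording and three recorded items; eligibility is unchanged. The downside is a smaller naive set. At SD 15, with patients removed equally from both groups, power for 20 points is 99.6% with half removed, so the planned power survives unless well over half are pre-exposed.

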3.2 Exclusion Criteria

1. Patient must not be pregnant or nursing.
2. The patient must not have acute promyelocytic leukemia or t(15;17) observed by FISH.
3. Patient must not have known CNS leukemia.
4. Patient must not have a history of positive HIV serology.
5. Patient must not have a history of positive Hepatitis C serology.
6. Patient must not have undergone a prior allogeneic stem cell transplant.
7. Patient must not have any uncontrolled intercurrent illness including, but not limited to, ongoing or active infection, ongoing or active GVHD, congestive heart failure of NYHA class 3 or 4, unstable angina pectoris, cardiac arrhythmia, or psychiatric illness/social situation that would limit compliance with study requirements.
8. Patient must not have had radiation therapy within 14 days of enrollment.
9. Patient must not have received any chemotherapy within 21 days of enrollment, and any acute treatment-related toxicities must have returned to baseline. Patients

may be receiving hydra at time of enrollment.

3.3 Inclusion of Women and Minorities

Both men and women and members of all races and ethnic groups are eligible for this trial.

4.0 REGISTRATION PROCEDURES

Patients must not start any protocol intervention prior to registration through the Siteman Cancer Center.

The following steps must be taken before registering patients to this study:

1. Confirmation of patient eligibility by Washington University
2. Registration of patient in the Siteman Cancer Center database
3. Assignment of unique patient number (UPN)

Once the patient has been entered in the Siteman Cancer Center OnCore database, the WUSM coordinator will forward verification of enrollment and the UPN via email.

4.1 Confirmation of Patient Eligibility

Confirm patient eligibility collecting the information listed below and scanning and emailing it to the research coordinator listed in the *Siteman Cancer Center Clinical Trials Core Protocol Procedures for Secondary Sites* packet at least one business day prior to registering patient:

1. Your name and contact information (telephone number, fax number, and email address)
2. Your site PI's name, the registering MD's name, and your institution name
3. Patient's race, sex, and DOB
4. Three letters (or two letters and a dash) for the patient's initials
5. Currently approved protocol version date
6. Copy of signed consent form (patient name may be blacked out)
7. Planned date of enrollment
8. Completed eligibility checklist, signed and dated by a member of the study team
9. Copy of appropriate source documentation confirming patient eligibility

4.2 Patient Registration in the Siteman Cancer Center OnCore Database

Registrations may be submitted Monday through Friday between 8am and 5pm CT. Urgent late afternoon or early morning enrollments should be planned in advance and coordinated with the Washington University research coordinator. Registration will be confirmed by the research coordinator or his/her delegate by email within one business day. Verification of eligibility and registration should be kept in the patient chart.

All patients at all sites must be registered through the Siteman Cancer Center OnCore database at Washington University.

4.3 Assignment of UPN

Each patient will be identified with a unique patient number (UPN) for this study. Patients

will also be identified by first, middle, and last initials. If the patient has no middle initial, a dash will be used on the case report forms (CRFs). All data will be recorded with this identification number on the appropriate CRFs.

5.0 INVESTIGATIONAL PLAN

5.1 Summary of Study Design

This is an open-label, single-arm, Phase II, biomarker study of patients with AML or MDS who are treated with 10 consecutive days of decitabine. FAB-M3 AML is excluded from this trial, because other well-tolerated options exist for the treatment of FAB-M3 acute promyelocytic leukemia. AML patients who are < 60 years old and have not received cytotoxic induction chemotherapy are also excluded, because cytotoxic therapy offers a curative possibility for these patients. MDS patients without cytopenias are also excluded because these patients can be followed with watchful-waiting.

All patients will undergo bone marrow biopsies pre-study, on Cycle 1 Day 10 \pm 1, and on Day 28 \pm 4 of Cycles 1, 2, 4, and 6. Following Cycle 6, bone marrow biopsies should be performed at the discretion of the treating physician to assess for relapse or progression. Patients will provide a skin biopsy sample pre-study. See Section 8.0 for details on correlative studies.

Patients will receive decitabine 20 mg/m²/day as a 1-hour infusion on consecutive Days 1-10 in 28-day cycles. The dose will be calculated based on actual patient weight at the beginning of each cycle.

Once AML patients achieve morphologic complete remission with incomplete blood count recovery (CRi) or MDS patients achieve a marrow complete response (Marrow CR) as defined in Section 9.0, decitabine administration may be decreased to 20 mg/m²/day for ten consecutive days every 6 weeks, to limit myelosuppressive toxicity and improve count recovery. After 2 cycles at 6 week intervals, the dose may be reduce to 20 mg/m²/day for five consecutive days in 6 week cycles, at the discretion of the treating physician. After two cycles of five consecutive days of treatment, if the patient meets the definition of CR with complete cytogenetic response as defined in Section 9.0, administration may further be decreased to three consecutive days per cycle at the discretion of the treating physician.

It will be a logistical goal of this trial consistently to return preliminary exome results to the treating physician by the end of Cycle 1 and validated results by the end of Cycle 2. However, this logistical goal is not a primary or secondary aim of this study. Given the limited data regarding mutation presence and drug response, we do not anticipate that the results will directly influence therapeutic decisions made by the treating physician. However, the development of comprehensive genomic pipelines and integration of this data into a clinical trial setting will be required before personalized medicine can be realized.

